#### **4.3.4 EBV-associated lymphoproliferative disorder**

The cumulative incidence of EBV-associated lymphoproliferative disorder or EBV reactivation therapy will be described using the Aalen-Johansen estimator, treating death as the competing risk. Cumulative incidence curves will be compared between treatments using Gray's test.

#### **4.3.5 Hyperglycemia**

Hyperglycemia is defined as a random glucose >200mg/dL or fasting glucose >126mg/dL and use of diabetes therapy, i.e. use of insulin and/or oral medications to control and/or maintain glucose level. The incidence of hyperglycemia and use of diabetes therapy at baseline, Day 28, and Day 56 will be estimated and compared between arms using a Z-test for comparing binomial proportions (or Barnard's Exact Unconditional Test as appropriate).

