#### 3.3.5. Steroid- and sirolimus- associated complications (collected in all patients):

# Incidence of hyperglycemia

Incidence of hyperglycemia (defined as a random glucose >200mg/dL or fasting glucose >126mg/dL) and use of diabetes therapy (use of insulin and/or oral medications to control and/or maintain glucose levels) at baseline, Day 28 and Day 56.

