#### 5. Incidence of hyperglycemia

Incidence of hyperglycemia and use of diabetes therapy at baseline, Day 28 and Day 56 will be estimated and compared between arms using a Z-test (or Barnard's Exact Unconditional as appropriate).

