##### **1.1.3 Exploratory Objectives**

The exploratory objectives of the study are to assess:

- Cumulative steroid dose (prednisone-equivalent) through Day 56 post randomization.

- Use of topical (skin, GI) agents for acute GVHD therapy at baseline and during the study's duration.
- Incidence of discontinuation of immune suppression, and immune suppression discontinuation without GVHD or disease progression/recurrence by Days 56, 180, and 365 post-therapy.
- Incidence of EBV-associated lymphoproliferative disorder or EBV reactivation requiring therapy
- Incidence of corticosteroid- and sirolimus-associated complications (collected in all participants):
- Incidence of hyperglycemia (defined as a random glucose >200mg/dL or fasting glucose >126mg/dL) and use of diabetes therapy (use of insulin and/or oral medications to control and/or maintain glucose levels) at baseline, Day 28 and Day 56.
- Hip Flexor and Quadriceps Strength score via handheld dynamometer at baseline, Day 56, and 6 months post-randomization
- Two Minute Walk Test score at baseline, Day 56, and 6 months post-randomization
- 5-time Sit-to-Stand Test score at baseline, Day 56, and 6 months post-randomization
- Adult Myopathy Assessment Tool (AMAT) score at baseline, Day 56, and 6 months post-randomization
- Incidence of hyperlipidemia as measured by fasting lipid panel at baseline, Days 28, 56 and 180 post-randomization.
- Incidence of post-transplant thrombotic microangiopathy (TMA) by 6 months post-randomization.
- Proportion of participants requiring therapy for CMV-reactivation by day 56 post-randomization.
- Change in patient-reported outcomes from enrollment to Day 56, 6 months and 12 months.
- MD Anderson Symptom Inventory (MDASI) score at baseline, Day 56, 6 months, and 12 months post-randomization
- FACT-BMT score at baseline, Day 56, 6 months, and 12 months post-randomization
- MOS Short Form 36 (SF-36) score at baseline, Day 56, 6 months, and 12 months post-randomization
- PedsQL (Pediatric participants) score at baseline, Day 56, 6 months, and 12 months post-randomization
- A secondary descriptive analysis will evaluate all study outcomes in AA3 participants.

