## **5. Template of Proposed Table/Figure/Listing (TFL) Shells**

Table/Figure/Listing titles and layout are for illustration purposes only, and may not be the final layout or wording chosen for publications or presentations. Actual format of the

tables and figures may differ and will be subject to change in the final analysis report and/or publication. See the Appendix of this SAP for the exhibit titles and shells.

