**Exhibit 1501-17: Hyperglycemia**

Hyperglycemia is defined as a random glucose >200mg/dL or fasting glucose >126mg/dL and use of diabetes therapy, i.e. use of insulin and/or oral medications to control and/or maintain glucose level.

Hyperglycemia by Treatment Group				
Assessment Time Point		Sirolimus (N=) N (%)	Prednisone (N=) N (%)	P-value*
Baseline	Yes	XX (XX.X%)	XX (XX.X%)	---
	No	XX (XX.X%)	XX (XX.X%)	
	Not Evaluable	XX	XX	
Day 28	Yes	XX (XX.X%)	XX (XX.X%)	X.XXX
	No	XX (XX.X%)	XX (XX.X%)	
	Not Evaluable	XX	XX	
Day 56	Yes	XX (XX.X%)	XX (XX.X%)	X.XXX
	No	XX (XX.X%)	XX (XX.X%)	
	Not Evaluable	XX	XX	

\* Clarify test used (Z test of binomial proportions or Barnard's Exact)

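### SAP 4.3.5 and Exhibit 1501-17 write diabetes therapy into the definition of hyperglycaemia, contrary to the protocol and SAP 1.1.3, and the only table shell has no row for therapy use

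*SAP*

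**What the plan says.** The protocol uses the same construction in its synopsis, in the exploratory objectives (2.3.3, item 5a) and in the endpoint definition (3.3.5). In 3.3.5 hyperglycaemia is "defined as a random glucose >200mg/dL or fasting glucose >126mg/dL) and use of diabetes therapy". The bracket closes after the glucose limits, so therapy use lies outside the definition. Protocol 5.2.6, item 5, then plans the analysis: "Incidence of hyperglycemia and use of diabetes therapy at baseline, Day 28 and Day 56 will be estimated and compared between arms".

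SAP 1.1.3 keeps the protocol form: "Incidence of hyperglycemia (defined as a random glucose >200mg/dL or fasting glucose >126mg/dL) and use of diabetes therapy".

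SAP 4.3.5 drops the bracket and turns the phrase into a definition: "Hyperglycemia is defined as a random glucose >200mg/dL or fasting glucose >126mg/dL and use of diabetes therapy". Its next sentence still treats the two as separate quantities: "The incidence of hyperglycemia and use of diabetes therapy at baseline, Day 28, and Day 56 will be estimated and compared between arms".

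Exhibit 1501-17 carries the same merged definition ("fasting glucose >126mg/dL and use of diabetes therapy, i.e. use of insulin and/or oral medications to control and/or maintain glucose level"). Its single table, "Hyperglycemia by Treatment Group", has one Yes / No / Not Evaluable block at each of baseline, Day 28 and Day 56. No row shows therapy use or glucose status on its own. SAP section 5 says of all the shells: "Table/Figure/Listing titles and layout are for illustration purposes only".

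**The concern.** SAP 1.5 sends the reader to the protocol and to SAP section 4 for endpoint definitions, and for this endpoint the two disagree. A programmer who codes 4.3.5 as written will not produce the protocol's rate. Because the sentence joins three conditions with an unbracketed *or* and *and*, two programmers could also produce different rates from each other.

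The patients lost are those with high glucose who are not yet on treatment. A patient whose glucose is controlled on insulin is also scored No, and the shell offers nowhere else to show that patient.

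The measure matters because steroid toxicity is among the trial's stated secondary interests (Protocol 2.1). Hyperglycaemia is the first of the corticosteroid- and sirolimus-associated complications in Protocol 2.3.3, and Protocol Table 1 lists it as a common sirolimus toxicity. Either arm can therefore be miscounted. SAP 4.3 tests the arms against each other at the 5% level on these outcomes.

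**Working it through.** The documents give no rate, sample size or power for this endpoint, so there is no stated figure to reproduce. The check is a comparison of definitions, followed by an illustration.

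**1. Who is counted.** Let R = random glucose above 200 mg/dL, F = fasting glucose above 126 mg/dL, T = use of diabetes therapy.

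| R | F | T | Protocol and SAP 1.1.3: R or F | SAP 4.3.5, grouping 1: (R or F) and T | SAP 4.3.5, grouping 2: R or (F and T) |
|---|---|---|---|---|---|
| 0 | 0 | 0 | No | No | No |
| 0 | 0 | 1 | No | No | No |
| 0 | 1 | 0 | **Yes** | No | No |
| 0 | 1 | 1 | Yes | Yes | Yes |
| 1 | 0 | 0 | **Yes** | No | Yes |
| 1 | 0 | 1 | Yes | Yes | Yes |
| 1 | 1 | 0 | **Yes** | No | Yes |
| 1 | 1 | 1 | Yes | Yes | Yes |
| | | **Yes count** | **6** | **3** | **5** |

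Grouping 1 loses all three untreated high-glucose combinations. Grouping 2 loses the one that is high on fasting glucose only and untreated. Neither grouping can exceed the protocol rate, and grouping 1 also cannot exceed the therapy-use rate.

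**2. One arm, assumed rates.** Suppose 40% are above a glucose limit and 30% are on therapy.

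- Grouping 1 counts the overlap. It lies between max(0, 0.40 + 0.30 − 1) = 0 and min(0.40, 0.30) = 0.30. The reported rate is 0% to 30% instead of 40%.
- Grouping 2: suppose 20 of the 40 points are fasting-only, and 20% to 80% of those patients are treated. The reported rate runs from 0.40 − 0.20 × (1 − 0.2) = 0.24 to 0.40 − 0.20 × (1 − 0.8) = 0.36, instead of 0.40.

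**3. Two arms, assumed rates, grouping 1.** The 60 per arm comes from SAP 2.1 and the two-sided 5% level from SAP 2.9 and 4.3. The true rates by the protocol definition are assumed to be 50% on prednisone and 25% on sirolimus. The reported rate in each arm is the true rate × the share of high-glucose patients who are treated. Power is for the pooled Z-test:

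power ≈ Φ[(|p₁ − p₂| − 1.96·√(2p̄(1−p̄)/60)) / √((p₁(1−p₁) + p₂(1−p₂))/60)], plus the far tail.

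For 0.50 vs 0.25, p̄ = 0.375. The null SE is √(2 × 0.375 × 0.625/60) = 0.0884 and the alternative SE is √((0.25 + 0.1875)/60) = 0.0854. Then (0.25 − 1.96 × 0.0884)/0.0854 = 0.90, which gives power 0.816.

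| Share treated, prednisone / sirolimus | Reported rates | Difference | Power |
|---|---|---|---|
| Protocol definition | 50% vs 25% | 25 points | 0.816 |
| 60% / 90% | 0.50 × 0.6 = 30% vs 0.25 × 0.9 = 22.5% | 7.5 points | 0.153 |
| 75% / 75% | 37.5% vs 18.75% | 18.75 points | 0.630 |
| 80% / 40% | 40% vs 10% | 30 points | 0.975 |

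The difference can shrink or widen, depending on how the treated share differs between arms.

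**The case against.** The strongest reply is that this is a lost pair of brackets with a limited reach. SAP 1.1.3 keeps the protocol form, and the analysis sentence of 4.3.5 still calls for therapy use to be estimated and compared. The shells are open to change, and no decision rests on the endpoint. All of that is true, and it limits the weight of the point. It does not resolve the conflict: the analysis sentence uses a term that has just been defined with therapy inside it, and the merged definition stands in the SAP body, not only in the shell.

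A second reply is that a composite may have been intended, counting a patient with high glucose or on therapy. Such a union would count seven of the eight combinations. With the one-arm margins above it would give between max(0.40, 0.30) = 40% and 0.40 + 0.30 = 70%, so the error would be upward. But the SAP sentence does not say this. For hyperlipidaemia, SAP 4.3.7 writes *and/or* when it combines a laboratory result with drug use; 4.3.5 does not, and it explains no change of definition. That a union is conceivable at all is a further reason to settle the wording.

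Two smaller points stand. The protocol puts both quantities under one lettered item and one heading, and never says in so many words that there are two tests; separate analysis is the natural reading of 5.2.6, not an explicit instruction. And the treated shares in the power table are chosen, with no support in the documents.

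**Conclusion.** The concern holds. SAP 4.3.5 and Exhibit 1501-17 state a rule that gives a different endpoint from Protocol 3.3.5 and SAP 1.1.3, and 4.3.5 is inconsistent within itself. The firm result is the classification: three or five combinations counted where the protocol counts six. It needs no assumption beyond reading the sentence as written. The percentages and power values rest on assumed glucose and therapy rates; they show only that the distortion could be material and that its direction in the arm comparison is unknown. The current shell shows no therapy-use row, although the SAP text still asks for that comparison. The correction should be made, with modest weight: the endpoint is exploratory, and the primary and key secondary analyses are not touched.

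**What to change.** Before data lock, define hyperglycaemia in SAP 4.3.5 and in the text of Exhibit 1501-17 as a random glucose above 200 mg/dL or a fasting glucose above 126 mg/dL, with nothing further in the definition. State that use of diabetes therapy (insulin and/or oral agents) is estimated and compared as a separate item at the same three visits, and add a Yes / No / Not Evaluable block for it to the exhibit. If a combined measure is also wanted, name it as an additional item and write its logic out in full.

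The cost is one reworded definition in two places, one sentence on therapy use and one extra block of table rows. No new endpoint is created, since Protocol 3.3.5 and SAP 1.1.3 already contain both items.

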#### **4.3.6 Functional Myopathy**

The change from baseline in functional myopathy score at Day 56 and 6 months post-randomization will be evaluated.

Functional Myopathy measures considered are:

- Hip Flexor and Quadriceps Strength via handheld dynamometer
- Two Minute Walk Test
- 5-time Sit-to-Stand
- Adult Myopathy Assessment Tool (AMAT)

These measures will be described for each treatment group at baseline, Day 56, and 6 months using medians and ranges. Change from baseline within treatment group will be assessed using a Wilcoxon Signed Rank test at each timepoint. Change from baseline at each timepoint will be compared between treatment groups using a Wilcoxon Rank Sum test.

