# 2.5. Treatment Plan

#### 2.5.1. Randomization

A 5 mL blood sample (red top tube) for Ann Arbor Scoring must be collected from the patient prior to enrollment/randomization in AdvantageEDC (see section 2.5.2). Upon confirmation of eligibility in AdvantageEDC, the study participant will be randomized in a 1:1 fashion to receive either sirolimus or prednisone. Study treatment (sirolimus/prednisone) should be initiated as soon as possible after randomization. A maximum of 24 hours from randomization to first dose of study medication is allowable.

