#### Post-Randomization

The following post-randomization assessments are required of all patients, regardless of therapy received.

- 1. Karnofsky or Lansky performance status at Days 56, 90, 180 and 365
- 2. Complete acute GVHD staging and grading information including assessments of rash, diarrhea, nausea/vomiting, weight and liver function tests weekly through Day 56; Day 90, 6 and 12 months
- 3. Chronic GVHD evaluation (if present) Day 28, 56, 90, and 6 and 12 months
- 4. CBC with differential, chemistry (including liver function tests) weekly through Day 56; Day 90, 6, and 12 months
- 5. Fasting lipid profile at Day 28, 56, and 6 months
- 6. Toxicity evaluation weekly through Day 56; Day 90, 6 months and 12 months
- 7. Recording of all systemic immune suppression, including steroid dose and drug levels (as appropriate for sirolimus, cyclosporine, tacrolimus) weekly through Day 56, Day 90, 6, and 12 months. Second-line immune suppressive therapy (therapy beyond initial

randomized therapy of either sirolimus or prednisone) should be recorded at each of these time points.

- 8. Use of topical (skin, GI) steroid agents weekly through Day 56; Day 90, 6 and 12 months.
- 9. Data on systemic infections, and EBV PTLD (or EBV requiring therapy), recorded as per the BMT CTN (Technical) MOP through 12 months.
- 10. EBV & CMV monitoring as per institutional practice.
- 11. Myopathy assessments at Day 56 and 6 months.\*
  - a. Hip Flexor and Quadriceps Strength via handheld dynamometer
  - b. Two Minute Walk Test
  - c. 5-time Sit-to-Stand
  - d. Adult Myopathy Assessment Tool (AMAT)
- 12. Patient reported outcomes (M.D. Anderson Symptom Inventory, FACT-BMT, SF-36, or PedsQL (Pediatrics)) at Day 56, 6 months and 1 year.\* Only English speaking adult and pediatric patients, and Spanish speaking adult patients are eligible to participate in the Health Quality of Life (HQL) component of this trial. Patients >18 years will complete the FACT-BMT, MOS SF-36 and MDASI instruments. Patients ≥ 8 years through 18 years will complete the PedsQLTM Stem Cell Transplant Module.
- 13. OPTIONAL 30-40 mL blood samples for research laboratory studies at Day 7, 28, and 56 (see Appendix B).\* Patients with weight <13 kg will have ≤3 mL/kg collected at each individual time point.

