#### Table 4.4 – REQUIRED ASSESSMENTS

	Pre- Randomize	Pre- Pre- Days Post Randomization											
	Base	line	7*	14*	21*	28*	35*	42*	49*	56 *	90**	180***	365***
History and physical exam	Х												
Pregnancy test (if applicable)	Х												
Karnofsky/Lansky performance status		Х								Х	Х	Х	Х
Acute GVHD evaluation	Х		Х	Х	Х	Х	Х	Х	Х	Х	Х	Х	Х
Chronic GVHD evaluation						Х				Х	Х	Х	Х
CBC with differential, platelet count	Х		Х	Х	Х	Х	Х	Х	Х	Х	Х	Х	Х
Basic chemistry (creatinine)	Х		Х	Х	Х	Х	Х	Х	X-	Х	Х	Х	Х
Liver function tests (alkaline phosphatase, bilirubin, AST, ALT)	Х		Х	Х	Х	Х	Х	Х	Х	Х	Х	Х	Х
Fasting lipid profile		X 				Х				Х		Х	
Toxicity and AE evaluation		Х	Х	Х	Х	Х	Х	Х	Х	Х	Х	Х	Х
Recording of all systemic immune suppression, including steroid dose	Х		Х	Х	Х	Х	Х	Х	Х	Х	Х	Х	Х
Drug level monitoring (e.g. tacrolimus, cyclosporine)	Х	Х	Х	Х	Х	Х	Х	Х	Х	Х	Х	Х	Х
Use of second-line immune suppressive therapy			Х	Х	Х	Х	Х	Х	Х	Х	Х	Х	Х
Use of topical agents	Х		Х	Х	Х	Х	Х	Х	Х	Х	Х	Х	Х
Malignancy relapse, death			Х	Х	Х	Х	Х	Х	Х	Х	Х	Х	Х
Systemic infections	Х		Х	Х	Х	Х	Х	Х	Х	Х	Х	Х	Х
EBV PTLD, or EBV requiring therapy			Х	Х	Х	Х	Х	Х	Х	Х	Х	Х	Х
CMV reactivation requiring therapy			Х	Х	Х	Х	Х	Х	Х	Х			
Myopathy assessments		X 								Х		Х	
Patient-reported outcomes: MDASI, FACT-BMT, MOS SF-36, PedsQL 		Х								Х		Х	Х
REQUIRED 5 mL blood sample for Ann Arbor Panel Scoring collection	X 												
OPTIONAL Research blood samples for ancillary studies (see Appendix B) 		Х	Х			Х				Х			

\* +/- 3 days to allow for scheduling flexibility, holidays, etc. Subsequent visits through Day 56 must be scheduled weekly.

\*\* +/- 14 days to allow for scheduling flexibility

\*\*\* +/- 28 days to allow for scheduling flexibility

 The fasting lipid panel may be done up to 96 hours after enrollment.

 Myopathy assessments may be done up to 96 hours after enrollment.

 Only English speaking adult and pediatric patients, and Spanish speaking adult patients are eligible to participate in the Health Quality of Life (HQL) component of this trial. Patients >18 years will complete the FACT-BMT, MOS SF-36 and MDASI instruments. Patients > 8 years through 18 years will complete the PedsQLTM Stem Cell Transplant Module.

 Required blood sample for Ann Arbor Scoring must be collected prior to enrollment/randomization and shipped overnight immediately afterwards.

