#### 5.2.6. Analysis of Exploratory Endpoints

The following endpoints and subgroup analyses are considered exploratory and will be analyzed at a significance level similar to the secondary endpoints.

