## **3. Participant Characteristics and Compliance**

### **3.1 Demographics and Baseline Characteristics**

Descriptive statistics for demographics and baseline characteristics of participants and donors will be presented by treatment group. Characteristics to be examined are: age, gender, race/ethnicity, performance status, primary disease, risk status, transplant conditioning regimen characteristics, donor type, HLA matching, graft source, initial GVHD prophylaxis delivered, donor and recipient CMV status, acute GVHD organ staging and overall grade at enrollment, and topical steroid therapy use.

Data on performance status, primary disease, risk status, conditioning regimen characteristics, donor type, HLA matching, graft source, initial GVHD prophylaxis, and

donor and recipient CMV status will be retrieved from the CIBMTR database. All other variables will be collected on clinical forms.

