**Exhibit 1501-18: Functional Myopathy**

Functional myopathy measures considered are:

- Hip Flexor and Quadriceps Strength via handheld dynamometer
- Two Minute Walk Test
- 5-time Sit-to-Stand
- Adult Myopathy Assessment Tool (AMAT)

Functional Myopathy Scores by Treatment Group								
Measure	Assessment Time	Sirolimus (N=)			Prednisone (N=)			Treatment Comparison p-value 
		N	Median (Range)	p-value 	N	Median (Range)	p-value 	
Hip Flexor and Quadriceps Strength	Baseline	XX	XX.X (XX.X, XX.X)	-	XX	XX.X (XX.X, XX.X)	-	-
	Day 56	XX	XX.X (XX.X, XX.X)	X.XXX	XX	XX.X (XX.X, XX.X)	X.XXX	X.XXX
	6 months	XX	XX.X (XX.X, XX.X)	X.XXX	XX	XX.X (XX.X, XX.X)	X.XXX	X.XXX
Two Minute Walk Test	Baseline	XX	XX.X (XX.X, XX.X)	-	XX	XX.X (XX.X, XX.X)	-	-
	Day 56	XX	XX.X (XX.X, XX.X)	X.XXX	XX	XX.X (XX.X, XX.X)	X.XXX	X.XXX
	6 months	XX	XX.X (XX.X, XX.X)	X.XXX	XX	XX.X (XX.X, XX.X)	X.XXX	X.XXX
5-time Sit-to-Stand	Baseline	XX	XX.X (XX.X, XX.X)	-	XX	XX.X (XX.X, XX.X)	-	-
	Day 56	XX	XX.X (XX.X, XX.X)	X.XXX	XX	XX.X (XX.X, XX.X)	X.XXX	X.XXX
	6 months	XX	XX.X (XX.X, XX.X)	X.XXX	XX	XX.X (XX.X, XX.X)	X.XXX	X.XXX
Adult Myopathy Assessment Tool	Baseline	XX	XX.X (XX.X, XX.X)	-	XX	XX.X (XX.X, XX.X)	-	-
	Day 56	XX	XX.X (XX.X, XX.X)	X.XXX	XX	XX.X (XX.X, XX.X)	X.XXX	X.XXX

	6 months	XX	XX.X (XX.X, XX.X)	X.XXX	XX	XX.X (XX.X, XX.X)	X.XXX	X.XXX
--	----------	----	-------------------------	-------	----	-------------------------	-------	-------

 Wilcoxon Signed Rank test comparing score change from baseline within treatment

 Wilcoxon Rank Sum test comparing score changes from baseline between treatments

*Clarify the population for the endpoint (n=?). If n is not the same as the primary endpoint, explain why (e.g. patient not evaluable, missing data, etc.)*

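### Functional myopathy (exploratory): the between-arm rank-sum test on raw change ignores the baseline value already collected, which loses precision unless the slope of follow-up on baseline is close to 1

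*SAP*

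**What the plan says.** Four tests (dynamometer strength, Two Minute Walk Test, 5-time Sit-to-Stand and AMAT) are done at baseline, Day 56 and 6 months. For the comparison of arms, SAP 4.3.6 states: "Change from baseline at each timepoint will be compared between treatment groups using a Wilcoxon Rank Sum" test. Protocol 5.2.6 item 6 plans the same test, and footnote 2 of SAP Exhibit 1501-18 reads "Wilcoxon Rank Sum test comparing score changes from baseline between treatments". None of these places includes a covariate. Item 6 says that patients with available data will be assessed first, but no later analysis is specified.

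The endpoint's standing is clear from the opening of Protocol 5.2.6: "The following endpoints and subgroup analyses are considered exploratory". SAP 2.9 sets two-sided tests at 5%, and SAP 4.3 applies no multiplicity control.

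Three other places bear on the point:
- **Age.** Age is available (SAP 3.1: "Characteristics to be examined are: age, gender, race/ethnicity, performance status"). The post-randomization myopathy tests have no age limit (Protocol 4.4: "The following post-randomization assessments are required of all patients, regardless of therapy received"). The questionnaires do have an adult cut-off: "Patients >18 years will complete the FACT-BMT, MOS SF-36 and MDASI instruments".
- **Baseline timing.** Protocol Table 4.4 allows a late baseline: "Myopathy assessments may be done up to 96 hours after enrollment".
- **Dosing.** Protocol 2.5.1 sets the start of treatment: "A maximum of 24 hours from randomization to first dose of study medication is allowable".

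**The concern.** Subtracting the baseline fixes its coefficient at 1. When the true slope of follow-up on baseline is not 1, part of the baseline's noise stays in the change score, or too much is removed, and the comparison of arms is less precise than it could be. Regression estimates the coefficient instead of fixing it.

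What is at stake is modest. Myopathy is one of several steroid-complication measures in a trial whose hypothesis includes a lower steroid burden. Protocol 4.4 marks these tests as outside standard of care, so patients perform them for this trial. At most 60 patients per arm are planned, and fewer will have both a baseline and a follow-up value. Losing precision that a recorded covariate could recover is avoidable.

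**Working it through.** **Inputs from the documents.** 60 AA1/2 patients per arm before missing data (SAP 2.1), 1:1 allocation, two-sided 5%. No power, SD, effect size or correlation is stated for myopathy, so there is no planned figure to reproduce for this endpoint.

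**Assumptions.** Let ρ be the correlation of baseline and follow-up, and k = SD(follow-up)/SD(baseline). Neither is given, so both are varied. Baseline variance is set to 1.

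**Formulas.**
- Var(change) = 1 + k² − 2ρk
- Var(baseline-adjusted) = k²(1 − ρ²)
- Loss of precision = 1 − Var(adjusted)/Var(change) = (1 − ρk)² / (1 + k² − 2ρk)

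The loss is zero when the slope ρk equals 1. With k = 1 the variance ratio reduces to (1 + ρ)/2.

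**Results.**

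| ρ | k = 0.8 | k = 1 | k = 1.25 |
|---|---|---|---|
| 0.3 | 0.5776/1.16 = 50% | 0.49/1.4 = 35% | 0.3906/1.8125 = 22% |
| 0.5 | 0.36/0.84 = 43% | 0.25/1 = 25% | 0.1406/1.3125 = 11% |
| 0.7 | 0.1936/0.52 = 37% | 0.09/0.6 = 15% | 0.0156/0.8125 = 1.9% |
| 0.8 | 0.1296/0.36 = 36% | 0.04/0.4 = 10% | 0 |
| 0.9 | 0.0784/0.20 = 39% | 0.01/0.2 = 5% | 0.0156/0.3125 = 5% |

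With k = 1, 60 patients per arm carry the information of 60 × (1 + ρ)/2 = 39, 45, 51 and 57 at ρ = 0.3, 0.5, 0.7 and 0.9. At k = 1.25 and ρ = 0.9 the slope is 1.125, so the loss returns even though the correlation is high.

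**Simulated power.** These runs use adults only, bivariate normal data, equal SDs and 45 per arm (an assumed evaluable number). The effect is set near 80% power for a normal-theory adjusted analysis.

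| ρ | Rank-sum on change | Normal-score regression |
|---|---|---|
| 0.3 | 59% | 79% |
| 0.5 | 66% | 79% |
| 0.7 | 71% | 79% |
| 0.9 | 75% | 78% |

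Type I error was about 5% for both. At k = 1.25 the gain nearly vanishes: 77.6% vs 79.4% at ρ = 0.7, and 78.4% vs 79.5% at ρ = 0.8.

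**Post-dose baselines.** If 10% of the effect is assumed to be present already in every baseline (equal SDs, no children), power is 50% vs 75%, 56% vs 73%, 61% vs 71% and 66% vs 70% at ρ = 0.3, 0.5, 0.7 and 0.9. Both analyses lose power and the regression stays ahead.

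**The case against.** The strongest reply is that nothing here is an error. The test is valid, the three places agree, the endpoint is exploratory and unpowered, and SAP 2.9 already allows an added analysis to be documented in the final report. All of that stands, and it is why this is an optional improvement. Naming the covariates in advance is still better than choosing them once data are seen.

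Four further objections hold in part:
- **Correlation alone does not settle the loss.** It depends on the slope, so the equal-SD figures bound it in neither direction.
- **Not all of the power gain comes from baseline.** Moving from Wilcoxon to normal scores accounts for about 1 to 3 points when data are normal. At ρ = 0.9 with equal SDs, one run gave 76.0% for the rank-sum test, 77.5% for unadjusted normal scores and 79.5% for the adjusted test.
- **The gain is not universal.** With heavy-tailed errors at ρ = 0.9, the rank-sum test had 87.0% power and the regression 86.8%.
- **Missing data may matter more.** The analysis uses available cases. Expected Day 56 mortality is 13.1% in standard-risk patients including AA3 (Protocol 5.2.2.2), and the weakest patients may miss testing. Baseline adjustment does not cure this.

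A reader might infer that the planned test is invalid or biased between arms. The documents do not support that: allocation is randomized, and the simulated type I error is about 5%.

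**Conclusion.** The point holds as a low-cost gain in precision on an exploratory endpoint. Under equal SDs the loss runs from 35% at ρ = 0.3 to 5% at ρ = 0.9. Over the same correlations it is about 0-22% at an SD ratio of 1.25 and about 36-50% at 0.8. The documents cannot say which case applies, so the gain may be large or close to nil.

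The validity statement assumes randomization with complete data. The power figures also assume 45 evaluable patients per arm and, except where noted, normal data with equal SDs.

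Two stronger readings should be resisted. One is that adjustment always wins; it does not when the slope is near 1, or with heavy tails at high correlation. The other is that a trial conclusion is at risk; no primary, key secondary or safety conclusion depends on this test.

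**What to change.** In SAP 4.3.6, Exhibit 1501-18 footnote 2 and Protocol 5.2.6 item 6, replace the between-arm comparison at Day 56 and at 6 months with the following, for each test:

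- **Model.** A linear regression whose outcome is the change from baseline, converted to normal scores of its ranks over all patients. The terms are arm, baseline value (also as normal scores) and age group (≤18, >18 years, following the questionnaire cut-off). Drop the age term if a group is empty or nearly so. Test the arm term two-sided at 5%.
- **Keep.** The rank-sum test as supportive, and the medians and ranges as the description.
- **Add.** A sensitivity analysis restricted to patients whose baseline test was done before the first dose. The 96-hour window can put a baseline after up to several days of treatment.

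The cost is wording edits, with the protocol change left to the next amendment, and slightly more analysis work. No new data are needed. The drawbacks are a coefficient without a clinical unit, little or no gain when the slope is near 1, and no remedy for values missing through death or weakness.
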